5.0 TREATMENT PLAN

5.1 EXPERIMENTAL DESIGN SYNOPSIS

The study is designed as a prospective Phase 1 trial of SLM and axitinib in adult patients with advanced or metastatic clear cell renal cell carcinoma, who have had at least one standard treatment including tyrosine kinase inhibitors (TKI) or mammalian target of rapamycin inhibitors (mTOR-I). There must be imaging confirmation of tumor progression after completing a course of standard treatment. SLM and Axitinib will be provided through the study. The information below regarding the dose levels is not applicable to the Pilot phase.

Dose Levels for Escalation and Expansion Phases	Selenium in the chemical composition of SLM	Axitinib
-2	1500 µg administrated orally twice daily for 14 days followed by 1500 µg once daily in combination with axitinib	5 mg oral twice daily with titration according to package insert (listed in this protocol 5.1 Experimental Design Synopsis)
-1	2500 µg administrated orally twice daily for 14 days followed by 2500 µg once daily in combination with axitinib	5 mg oral twice daily with titration according to package insert (listed in this protocol 5.1 Experimental Design Synopsis)
0	3000 µg administrated orally twice daily for 14 days followed by 3000 µg once daily in combination with axitinib	5 mg oral twice daily with titration according to package insert (listed in this protocol 5.1 Experimental Design Synopsis)
1 (starting dose)	4000 µg administrated orally twice daily for 14 days followed by 4000 µg once daily in combination with axitinib	5 mg oral twice daily with titration according to package insert (listed in this protocol 5.1 Experimental Design Synopsis)

**All dose levels: starting on day 15, SLM will be taken once daily in combination with axitinib.

Escalation Part 1: COMPLETED: Last patient enrolled 10/23/2018.

Patient will start the assigned dose of SLM for 14 days and then will resume taking SLM orally at the same dose, combined with axitinib 5 mg twice daily with titration according to package insert (listed in this protocol 5.1 Experimental Design Synopsis).

Safety assessment will follow the guidelines provided in the National Cancer Institute Common Terminology Criteria for Adverse Events (NCI-CTCAE) Version 4.03.

Patients will be followed both clinically and radiographically (CT) at baseline then every 8 weeks after starting the treatment. Responses will be assessed using RECIST 1.1 criteria. Dose level 1 (4000 µg) will be the starting dose in the standard 3+3 dose escalation design. Three patients will be recruited for Dose level 1.

The next three patients will be recruited for Dose level -1 (2500 µg). While none of the three patients in Dose level 1 experienced a DLT, there were significant side effects. If 0 of three patients at Dose level -1 experiences a DLT related to SLM, then dose escalation will proceed to the next dose level (3000 µg).

If one of the three patients at Dose level -1 experiences a DLT related to SLM, then three more patients will be treated at the same dose. If exactly one out of six patients experiences a DLT, then dose escalation will proceed to the next dose level (3000 µg) after discussion at the weekly SLM meeting.

If two of the first three patients experience DLT related to SLM, then the dose will de-escalate to the lower dose (1500 µg).

The next patient can be enrolled after the previous patient's 28th Day of SLM assessment, provided there are no DLTs related to SLM. The minimum number of patients required is 6 and the maximum is 12.

Dose Limiting Toxicities:

DLTs related to SLM will be defined as any of the following events determined by the Investigator to be related to treatment combination irrespective of outcome. This applies to the first cycle only (2 weeks SLM alone + 4 weeks combination therapy):

- Clinically significant non-hematologic toxicity of Grade 3 or greater not related to underlying malignancy.
- Severe hematological toxicity (Grade 4 neutropenia, Grade 3-4 febrile neutropenia, or Grade 4 thrombocytopenia).
- If resolution of DLT related to SLM does not occur in 4 weeks, then patient will be withdrawn from the study.
- Grade 4 nausea, vomiting, diarrhea, or electrolyte imbalances or Grade 3 nausea, vomiting, diarrhea and electrolyte imbalances lasting greater than 48 hours despite optimal medical intervention.
- In the dose escalation phase, treatment delays related to the study drug that last >2 weeks

- Any grade 3 or higher DLT related to SLM alone will be discussed at the weekly SLM committee meeting.
-

Expansion Part 2: Enrollment Completed

After completing the Escalation Part 1 and based on the safety results, we will initiate an expanded cohort, Expansion Part 2 including a total of 19 patients with advanced metastatic CCRCC, to be treated with SLM 4000 in combination with axitinib 5 mg PO BID.

Up to 20 patients in the Expansion Part 2 and pilot phase will have mandatory biopsies at baseline before the start of SLM that will be repeated around day 14 (+/- 3 days) after starting SLM, at Cycle 3 (8 weeks +/- 3 days after first dose of SLM plus Axitinib) and preferably at disease progression, preferably from the same site of the previous biopsy, to study the expression of HIF-a and VEGF by immunohistochemistry (IHC), along with other biomarkers detailed in the correlative studies, before and after treatment with SLM. These tissues will be flash frozen and stored at -80 C to be processed later all at once for the proposed biomarkers.

The candidate patients for the biopsies will be chosen carefully by the treating oncologist and after discussion with the interventional/ body radiologist. Decision will be based on safety, ease of accessibility, tumor size and feasibility of getting the biopsy which can be done either on the primary renal tumor or metastatic site. Patient has to agree to get the biopsies, and sign consent form, after discussing the risks and benefits of the procedure with the provider.

All patients will have a peripheral blood draw at baseline before the start of SLM and repeated on day 14 after starting treatment. This blood will be stored and may be used later to study the protein expression of HIF1a, HIF2a, VEGF and level of SLM.

For Escalation Subjects: All patients will have a peripheral blood draw at baseline before the start of SLM and repeated on day 14 after starting treatment.

For Expansion Subjects: the peripheral blood draw will occur pre-dose and 2 hours post dosing on day 1 then 2 hours post dosing on Day 14 and at Cycles 2, 3, 4, 7, 10 and 13.

Pilot Phase: BSA based dosing. See additional details in protocol Section 14.4.

5.2

STUDY AGENT ADMINISTRATION

Treatment will be administered on an outpatient basis. Reported adverse events and potential risks are described in Section 8. Appropriate dose modifications are described in Section 7. No investigational or commercial agents or therapies other than those described below may be administered with the intent to treat the patient's malignancy. Treatment with SLM and axitinib will continue until disease progression or unacceptable toxicities or patient meets any criteria for removal from study as outlined in section 5.6.1. After completion of the SLM run-in period, each cycle will be 28 days in length.

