5.6.1 CRITERIA FOR REMOVAL FROM STUDY

Patients will continue study treatment until any of the following occur:

- Disease progression (treatment beyond progression at the discretion of treating provider with confirmatory scan in 8 weeks if the patient is clinically doing well).
- Unacceptable toxicity
- Intercurrent illness that prevents further safe administration of treatment
- Withdrawal of consent
- Serious protocol violation
- Non-compliance to therapy regimen
- General or specific changes in the patient's condition rendering the patient unacceptable for further treatment, in the judgment of the investigator

The reason for study removal and the date the patient was removed must be documented on the Case Report Form.

5.7 END OF TREATMENT:

The end-of-treatment visit is to be conducted 28 days (+/- 7 days) after treatment discontinuation, and will include the following assessments:

- Physical examination
- Vital signs including blood pressure
- Assessment of ECOG performance status
- Clinical Chemistries
- CBC with differential
- Glucose
- Urinalysis
- Assessment of adverse events
- Concomitant medications
- Mandatory Fresh Tumor Tissue Biopsy at disease progression, for up to 20 patients in Expansion and pilot Phase, if accessible and deemed safe by physician.

5.8 EVALUABLE POPULATIONS:

For Escalation Part 1: the DLT evaluable population includes all patients who complete one cycle of SLM and patients who experience a DLT during the first cycle of dosing.

For Escalation Part 1 and Expansion Part 2: The safety population includes all patients who receive at least one dose of SLM.

For Expansion and Pilot Phase: The evaluable population includes all patients who have measurable disease at screening, according to RECIST criteria for the relapsed solid tumor cohort and undergo a baseline disease assessment and at least one on-treatment disease assessment. Evidence of disease progression including radiological assessments, hematological assessments, death due to disease progression, and study drug withdrawal due to disease progression will be counted as post-baseline disease assessments. Evaluation for clinical response will include only those with measurable disease at baseline and evaluation of progression will be evaluated in all patients regardless of measurable disease status at baseline.

6.0 SAFETY ASSESSMENTS:

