14.3 ANALYSIS OF STUDY ENDPOINTS

14.3.1 Analysis of primary endpoint

a. The safety profile of the SLM and axitinib combination will be assessed by listing the overall incidence of AEs. The AEs will be summarized and classified by body system and by treatment group. The type, incidence, severity, and causality of each AE, the duration of the event, and any required treatment interventions will be tabulated. Physical examination results will be presented in the patient data listings. The DLT will be listed per dose level and treatment along with overall frequencies. The data from the expansion part will be used for this part of safety and tolerability assessment.

b. (Recommended Part 2 dose)

Dose level 1 (4000 µg) will be the starting dose in the standard 3+3 dose escalation design. Three patients will be recruited for Dose level 1.

The next three patients will be recruited for Dose level -1 (2500 µg). While none of the three patients in Dose level 1 experienced a DLT, there were significant side effects.

If 0 of three patients at Dose level -1 experiences a DLT related to SLM, then dose escalation will proceed to the next dose level (3000 µg).

If one of the three patients at Dose level -1 experiences a DLT related to SLM, then three more patients will be treated at the same dose. If exactly one out of six patients experiences a DLT, then dose escalation will proceed to the next dose (3000 µg) after discussion at the weekly SLM meeting.

If two of the first three patients experience DLT, then the dose will de-escalate to the lower dose (1500 µg).

The next patient can be enrolled after the previous patient's Day 28 assessment, provided there are no DLTs. The minimum number of patients required is 6 and the maximum is 12.

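### Part 1 permits the next dose level to open after the previous patient's Day 28 of SLM, with 14 of the 42 DLT-window days unobserved, and this is not reconciled with the window or the evaluability rule

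*Combined protocol and SAP*

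**What the plan says.** The relevant statements for Escalation Part 1 are these.

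- **DLT window (5.1, Dose Limiting Toxicities).** "This applies to the first cycle only (2 weeks SLM alone + 4 weeks combination therapy"). The combination begins after the run-in: "starting on day 15, SLM will be taken once daily in combination with axitinib" (5.1, note to the dose table). Section 5.2 adds: "After completion of the SLM run-in period, each cycle will be 28 days in length".
- **Enrolment gate.** Section 5.1: "The next patient can be enrolled after the previous patient's 28th Day of SLM assessment, provided there are no DLTs related to SLM". Section 14.3.1, item b: "The next patient can be enrolled after the previous patient's Day 28 assessment, provided there are no DLTs", without saying from which start Day 28 is counted.
- **Decision rule (5.1, repeated in 14.3.1b).** "If 0 of three patients at Dose level -1 experiences a DLT related to SLM, then dose escalation will proceed to the next dose level". Rules for 1 of 3, 1 of 6 and 2 of 3 follow. They are written out for the 2500 µg level only, and none says on which day the count is read.
- **Evaluability (5.8).** "the DLT evaluable population includes all patients who complete one cycle of SLM and patients who experience a DLT during the first cycle of dosing".
- **A DLT criterion that takes time to be met (5.1).** "In the dose escalation phase, treatment delays related to the study drug that last >2 weeks".
- **What happened.** Section 2.3 lists the cohorts in the order 4000, 2500, 3000, 4000 µg. Section 5.1 says Part 1 is complete and that Part 2 follows it, with 19 patients at 4000 µg.

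**The concern.** The gate is shorter than the window over which the event that it screens for is defined. It makes no distinction between the next patient in the same cohort and the first patient at the next level, and no separate wait is stated at cohort level. As written, a higher level can therefore open while the last patient of the level below is still inside the DLT window and, if DLT-free, not yet in the population that 5.8 calls evaluable.

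No rule says what follows if that patient then has a DLT on Days 29-42. The suspension rule in 7.1 is a different test: it depends on 10% or more of patients having grade 3 or higher events that are not controlled within 14 days.

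The protocol handles this better elsewhere. In the Pilot phase (14.4) DLTs are defined over Days 1-14, the model is updated after the Day 14 evaluation, and any DLT in that window pauses accrual for committee review. There the window and the decision point match and an event has a stated consequence.

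Defining the dose for Part 2 and for a later phase 2 trial is a primary objective (1.1). With Part 1 finished, what is at stake is how well the recorded decisions support that dose.

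**Working it through.** The plan states no operating characteristics for the Part 1 rule, so there is no figure to reproduce.

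**1. Calendar, from 5.1 and 5.2.**
- DLT window: 14 + 28 = 42 days.
- Combination days observed at the gate: 28 − 14 = 14 of 28, so 14 (50%) are unobserved.
- Window days unobserved at the gate: 42 − 28 = 14 of 42 (33%).

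**2. Who is affected.** Suppose patients enter back to back, each starting SLM on the previous patient's Day 29. When the third patient reaches Day 28, the second is at Day 56 and the first at Day 84. Both are past Day 42, so only the last patient of a cohort is incomplete. Any slower accrual shrinks the gap.

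**3. Which steps are affected.** The step after the first 4000 µg cohort went down, and Part 2 opens after Part 1 is completed. That leaves 2500 to 3000 µg and 3000 to 4000 µg.

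**4. Exposure at the new level.** If the new patient starts on the previous patient's Day 29, the previous patient's Day 42 is the new patient's Day 14. The earlier window closes before the new patient begins axitinib, but after up to 14 days of twice-daily SLM at the higher level.

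**5. The delay criterion.** A delay beginning on the first combination day (Day 15) first exceeds 14 days on Day 29. A delay arising in the combination period therefore cannot be recorded as a DLT by the gate.

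**6. Size for a 0/3 reading.** Let p be the true 42-day DLT rate and f the share of DLTs that fall after Day 28. Neither is in the documents, so both are assumptions. Take f = 1/3 (DLTs spread evenly over 42 days) or f = 1/2 (spread evenly over the combination period only).
- All three patients observed to Day 42: P(0/3) = (1 − p)³.
- Third patient read at Day 28: P(0/3) = (1 − p)² × [1 − p(1 − f)].
- Difference: (1 − p)² × p × f.

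| Assumed p | Full window | Read at Day 28, f = 1/3 | Read at Day 28, f = 1/2 | Rise, points |
|---|---|---|---|---|
| 0.10 | 0.729 | 0.756 | 0.769 | 2.7 to 4.1 |
| 0.20 | 0.512 | 0.555 | 0.576 | 4.3 to 6.4 |
| 0.33 | 0.301 | 0.350 | 0.375 | 4.9 to 7.4 |

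For example, at p = 0.33 and f = 1/2: 0.67² × 0.33 × 0.5 = 0.4489 × 0.165 = 0.074.

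These figures describe a count that is actually read at Day 28, which the text permits but does not prescribe.

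**The case against.** The strongest reply is that the gate governs enrolment, not the count. A reader might infer that the last patient of every cohort was counted as DLT-free at Day 28 and that the recommended dose therefore rests on understated DLT counts. The documents do not support that. No sentence closes the 3+3 count at Day 28. The counting rules use a DLT definition that spans six weeks, and 5.8 requires a completed cycle or a DLT. Nor can it be said of every cohort, because only two steps went up. Section 14.3.1a already lists DLTs by dose level, and 8.4 records all adverse events on study and for 30 days after the last dose, so a late DLT would be in the data. All of this stands.

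It can also be said that both upward steps led to doses no higher than 4000 µg, which three patients had already received without a DLT (5.1), and that the earlier window closes before the new patient starts the combination. Both are fair, and both limit the consequence. The same paragraph of 5.1 also reports significant side effects at that dose, and they preceded the step down.

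The delay criterion is weaker than it looks. The title section names SLM as the study drug, and a delay starting early in the run-in could be met by Day 28. The point holds only for delays that begin in the combination period.

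One might read Day 28 in 14.3.1b as Day 28 of the cycle after run-in. That would be study Day 42 and would remove the gap. Section 5.1 counts days of SLM and does not allow that reading.

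What remains unanswered is that no text ties the opening of the next level to the end of the window, or says what a DLT on Days 29-42 would then trigger.

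**Conclusion.** The concern holds in a limited form. Sections 5.1 and 14.3.1b permit the next level to open with 14 of 28 combination days unobserved in the last patient of the level below. This is not reconciled with the six-week window in 5.1 or the evaluability definition in 5.8. Two decisions are exposed.

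If the third patient was in fact read at Day 28, the chance of a 0/3 result rises by about 3-4 points at an assumed 10% DLT rate and 5-7 points at an assumed 33%. This rests on the assumed rates, the assumed timing of DLTs and back-to-back entry. Nothing in the documents shows that any patient at a higher level was enrolled before the previous patient's Day 42, or that any decision would have been different.

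**What to change.** The sponsor should reconcile the Day-28 gate in 5.1 and 14.3.1b with the six-week DLT window and with the evaluability definition in 5.8. Which of these governs is for the sponsor to settle.

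As Part 1 is complete, add to 14.3.1b that:
- DLTs per level will be tabulated over the full stated DLT window, with onset day and the evaluable denominator.
- The two upward decisions (2500 to 3000 µg and 3000 to 4000 µg) will be re-checked against the stated 3+3 rule on these counts.
- The report of the recommended dose will say whether the last patient of each cohort had completed the window when the next level opened, and whether any decision would have differed.

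The cost is a few lines of text and one re-tabulation of data already collected, with no new patients or visits. The possible downside is a less favourable DLT count at a level. If every window was complete when the next level opened, one sentence in the report settles the matter.

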5.3 SLM AND AXITINIB ADMINISTRATION

SLM oral capsules will be given twice daily alone for the first 14 days, then once daily in combination with Axitinib thereafter. SLM dosing will be based on patient BSA for the Pilot phase and tolerance based on DLT assessments during run-in only. See section 14.4 for dosing information for the Pilot portion. SLM will be provided by the study free of charge, by Sabisna Corporation located in NJ, USA. SLM will be stored in the Investigational Pharmacy at University of Iowa Hospitals and Clinics.

Axitinib oral tablets will be provided by the study free of charge from Pfizer and stored in the Investigational Pharmacy at the University of Iowa Hospitals and Clinics. Dosing will start at 5 mg twice daily, with the two doses taken 12 hours apart, with or without food. Axitinib will begin after the patient completes the 14 day SLM run-in portion of the trial.

Over the course of treatment, patients who tolerate Axitinib for at least two consecutive weeks with no adverse reactions >Grade 2 (according to the Common Toxicity Criteria for Adverse Events [CTCAE]) may have their dose increased as follows.

When a dose increase from 5 mg twice daily is recommended, the Axitinib dose may be increased to 7 mg twice daily, and further to 10 mg twice daily using the same criteria.

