5.5 DURATION OF FOLLOW-UP

Patients will be followed up, until they are lost to follow-up or death, whichever occurs first. Patients removed from study for unacceptable adverse event(s) will be followed for resolution or stabilization of the adverse event as well. Follow up off study will be performed using telephone contact correspondence with treating physicians, and death records as necessary to update vital status at least every 6 months.

5.6 EVALUATIONS DURING SCREENING AND TREATMENT:

The following evaluations and assessments will be performed at the specified times listed in the study calendar (section 11.0):

- Physical examination
- Vital signs including blood pressure with each visit
- Assessment of ECOG performance status
- Clinical Chemistries
- CBC with differential
- Urinalysis
- Glucose
- Erythropoietin levels
- Lipid Panel
- Coagulation levels
- Blood sample(s) for SLM concentration analysis, miRNA samples and additional blood for storage.
- Pregnancy test for women of childbearing potential.
- EKG
- Dual Energy CT Scans will occur at Screening, Day 14 and Cycle 3(8 weeks after first dose of SLM plus Axitinib)
- Disease assessments CT +/- Bone Scan will begin at Cycle 5 Day 1(every 8 weeks +/- 5 days). These scans will be performed as determined by the treating physician. If subject is asymptomatic, bone scans may be done every 4 months.
- Concomitant medications
- All treatment-related adverse events should be followed until resolution or stabilization.
- Safety phone call to assess subject status. Archival tumor tissue collection, if availableFresh Tumor Tissue Biopsy at Screening, Day 14 and Cycle 3 (+/- 3 days both occasions) and preferable at progression, for up to 20 patients in Expansion Phase and the Pilot phase, if accessible and deemed safe by physician.

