21.2 CT PROTOCOL

The same CT scan protocol will be obtained at 3 time points;

- Visit 1: baseline prior to treatment
- Visit 2: 14 ± 2 days following start of SLM
- Visit 3: 56 ± 3 days following start of chemotherapy (axitinib)

If for any reason baseline DECT could not be performed, we will utilize only regular CT scan subsequently in that setting (cancel further DECT) and there will NOT be a need for day 14 scan. This need to be discussed by PI before enrollment on study.

21.3 DUAL ENERGY CT:

- Contrast: 50% saline mixed with 50% 370mg/ml Iopamidol delivered at 4ml/s (4ml/s (35 s+ 5s) = 160ml of which 80ml is contrast) with delay of 35s (for chest) and 70s (for abdomen/pelvis)
- Positioning: Cranialcaudal acquisition with scan coverage (DFOV) from pubic symphysis to apex of lungs (DFOV to match prior visit). Acquisition at coached total lung capacity (TLC) (recorded for DECT)
- Acquisition: CHEST: The spiral DECT contrast scan with dose modulation with tube A: 120 ref mAs/80kV, tube B: 67 ref mAs/Sn150 kV, with a pitch of 0.55 and rotation time of 0.25sec. The CTDIvol is assumed to be 4.28mGy, with total DLP of 143.2mGy*cm for a 30cm scan.
- Acquisition: ABDOMEN: The spiral dual energy contrast abdomen/pelvis scan protocol uses dose modulation with tube A: 190 ref mAs/100kV, tube B: 95 ref mAs/Sn150 kV, with a pitch of 0.55 and rotation time of 0.25sec. The CTDIvol is assumed to be 10.41mGy, with total DLP of 553.7mGy*cm for a 50cm scan.
- Reconstruction: R1: 0.75 x0.5; R2: 2.0 x 1.4, Qr40(Admire 5), FOV to match prior visits, Energy Series: A, B and M. Keep Raw data.

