21.4 ANALYSIS

- Hypothesis: SLM will improve vascularization of tumors (ie increase in tumor iodine density at visit 2) which will allow for more effective chemotherapy treatment (ie decrease in tumor iodine density at visit 3, and decrease in tumor size). Secondary analysis may examine if baseline (visit 1) levels correlate with SLM response and/or treatment outcome (ie tumors with poor vascularization at visit 1, benefit more from SLM).

- Syngo via (initial analysis on 2.0x 1.4 recon) to produce virtual non-contrast image (VNC), mono energetic 40keV, Iodine concentration PBV (HU and mg/ml)
- Examine analysis results using fixed region of interest (ROI) in tumor volume vs semi-automatic tumor segmentation.

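### The Day-14 biopsy and dual-energy CT windows run past the Day-15 start of axitinib, so a compliant sample read as an SLM effect can follow axitinib exposure

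*Combined protocol and SAP*

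**What the plan says.** **Treatment sequence.** SLM is given alone, twice daily, for 14 days. The note to the dose table in section 5.1 then states: "starting on day 15, SLM will be taken once daily in combination with axitinib". Section 5.3 agrees: "Axitinib will begin after the patient completes the 14 day SLM run-in portion of the trial". The trigger for axitinib is the end of the run-in; neither section mentions completion of the biopsy, scan or blood draw.

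**Biopsy.** In up to 20 expansion and pilot patients, a baseline biopsy is "repeated around day 14 (+/- 3 days) after starting SLM". Section 5.6 repeats the tolerance: "Day 14 and Cycle 3 (+/- 3 days both occasions"). Section 5.1 gives the purpose as HIF and VEGF expression before and after SLM. Secondary objective 4 (section 1.2) asks whether the SLM dose alters HIF1a, HIF2a, VEGF and three microRNAs.

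**Dual-energy CT.** Section 21.2 lists "Visit 2: 14 ± 2 days following start of SLM", and section 21.1 gives the same tolerance. The hypothesis in section 21.4 is that "SLM will improve vascularization of tumors (ie increase in tumor iodine density at visit 2"), followed by a fall at visit 3, which section 21.2 places 56 ± 3 days after the start of axitinib.

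**Blood.** Section 5.1 has the draw "repeated on day 14 after starting treatment". Section 14.4 and tables 20.1 and 20.2 also say Day 14 without a tolerance. The study calendar (section 11.0) puts the run-in visits under a heading of plus or minus 2 days.

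**The concern.** The run-in is the only part of this single-arm trial in which SLM acts without axitinib. The Day-14 tissue and the visit-2 scan are therefore the only measurements that can separate the two drugs. Section 2.5 describes axitinib as a selective inhibitor of VEGF receptors 1, 2 and 3, so it acts on the pathway being measured. If a sample taken after axitinib has started is pooled with the Day-14 set, its change from baseline belongs to the combination but is reported as SLM's. The study hypothesis in section 2.7 is sequential: SLM lowers HIF and VEGF, and this sensitises the tumour to axitinib. It depends on that separation.

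**Working it through.** No power or sample-size figure is involved, and the plan states no figure to reproduce. The check is a day count.

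**Inputs**
- Axitinib start and change from twice-daily to once-daily SLM: Day 15 (sections 5.1 and 5.3).
- Biopsy tolerance: ± 3 days (sections 5.1 and 5.6).
- Dual-energy CT tolerance: ± 2 days (sections 21.1 and 21.2).
- Blood tolerance: none in the text or lab tables; ± 2 days if the calendar heading applies.
- Axitinib starting dose: 5 mg twice daily, so 2 doses per day.

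**Formula.** Window = target day ± tolerance. Overlap = number of window days on or after Day 15.

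The target can be read in two ways. If the first SLM dose is Day 1, the target is study Day 14. If the wording means 14 elapsed days after the first dose, the target is Day 15.

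| Procedure | Target Day 14: window | Overlap | Target Day 15: window | Overlap |
|---|---|---|---|---|
| Biopsy ± 3 | 11-17 | 3 of 7 (15, 16, 17) | 12-18 | 4 of 7 |
| Dual-energy CT ± 2 | 12-16 | 2 of 5 (15, 16) | 13-17 | 3 of 5 |
| Blood, if ± 2 applies | 12-16 | 2 of 5 | 13-17 | 3 of 5 |

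The study-day count is the more lenient one. On the elapsed-day count, even a procedure done exactly on target falls on Day 15.

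**Possible exposure at the upper limit (study-day count).** By the end of Day 17: 3 days × 2 = 6 axitinib doses. By the end of Day 16: 2 × 2 = 4 doses. These are maxima.

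**Which tolerance avoids the overlap.** With axitinib starting on Day 15, an upper limit of Day 14 + 0 stays SLM-only. Limits of + 1, + 2 and + 3 give Days 15, 16 and 17, all on or after the start.

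**Safeguards looked for.** The calendar and its footnotes (11.0), the secondary analysis (14.3.2) and the CT sections (21.1 to 21.4) contain no rule placing the procedures before the first axitinib dose, no flag for late ones and no exclusion. The calendar gives Cycle 1 its own ± 3 days, which could delay axitinib, but nothing ties that delay to an outstanding biopsy or scan.

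**The case against.** **The intent is clear.** The calendar lists the Day-14 work under the run-in, and axitinib follows completion of the run-in. Section 6.0 also wants a urinalysis before axitinib, and the calendar schedules one at Day 14. This stands as evidence of intent. It does not close the gap for a biopsy or scan booked separately under its own stated tolerance.

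**Late samples can already be identified.** The patient diary (Appendix C) records the date and clock time of each axitinib dose, and Appendix B has study-drug administration entered in the eCRFs. This stands: no new data item is needed, only a rule for using it.

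**The day counts are not sample counts.** A reader might infer from 3 of 7 and 2 of 5 that about 40% of samples are contaminated. The documents do not support that. The counts are shares of permitted days around a Day-14 target, and a Day-15 procedure could still precede the first dose. No late sample is documented.

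**The CT result might reverse.** A reader might infer this because section 21.4 expects iodine density to fall. That fall is expected at visit 3, about 56 days into axitinib; nothing is given for one or two days. What can be said is that any bias would tend to mask the hypothesised rise rather than create it.

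**Blood.** A reader might infer that the blood draw, and with it the pilot's dose-finding model, overlaps in the same way. Here the evidence is weaker: every text statement says Day 14, and the tolerance comes only from a calendar heading. The effect may also be small. Section 2.3 shows mean selenium from D14 to C2 rising 30 to 44, 14 to 21, 17 to 25 and 17.5 to 27 in the four cohorts. Assuming µM, linear change and C2 on study Day 43 (14 + 28 + 1), hence 29 days, the steepest slope is 14 / 29 = 0.48 per day. A 2-day slip is then about 1 µM against the 45 µM threshold. A brief dip after the change in SLM schedule is not excluded, but nothing shows one. What stands is an inconsistency to reconcile.

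**Conclusion.** The concern holds for the biopsy and the dual-energy CT. As worded, on the study-day count, 3 of 7 permitted biopsy days and 2 of 5 permitted CT days fall on or after the axitinib start, and the overlap is larger on the elapsed-day count. A fully compliant Day-14 sample can therefore carry an axitinib effect while being read as SLM's. For HIF, VEGF and microRNA the documents give no direction for such an effect.

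The overlap is permitted, not shown to have occurred. The affected measures are secondary or correlative and are analysed descriptively; PFS and safety are untouched. For blood, the finding is limited to conflicting statements of the window.

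This rests on axitinib starting on Day 15 as stated, and on the text examined, which lacked some pages, apparently from the lab manual (19.0) and section 21.7. A timing instruction there cannot be excluded.

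**What to change.** - **Windows.** In sections 5.1, 5.6, 11.0, 21.1 and 21.2, set the upper limit of the Day-14 biopsy and dual-energy CT window as before the first axitinib dose, and state that Day 1 is the day of the first SLM dose. This changes assessment timing only; no dose or treatment schedule changes.
- **Patients already sampled.** Use the recorded axitinib dose times to flag biopsies and scans that followed the first dose. Leave them out of the SLM-only comparison, or show results with and without them. Section 5.1 has the tissue stored for processing in one batch, so the rule can be written before any assays not yet run.
- **Blood.** Reconcile the calendar's ± 2 day run-in heading with the plain Day 14 in sections 5.1 and 14.4 and tables 20.1 and 20.2, so that the selenium value entering the pilot model is drawn before the Day-15 change in SLM schedule.

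**Cost.** In full days, on the study-day count, the biopsy window shrinks from 7 to 4 (Days 11-14) and the CT window from 5 to 3 (Days 12-14). That is a real constraint for interventional radiology, and exclusions would come from a biopsy set of at most 20 patients. Expansion enrolment is complete, so the new window can reach only pilot patients (10 planned); for expansion patients the gain comes from the analysis rule.
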